Virtual Reality for Improving Pain and Distress in Patients with Advanced Stage Colorectal Cancer

(VR Blue)

Pro00103248

NCT04069702

July 30, 2021

Purpose of the Study

Aim 1: Examine the feasibility, acceptability and safety of a 30-minute VR Blue session in patients with advanced colorectal cancer.

Hypothesis: Feasibility will be determined by accrual (N=20 patients over 6 months), >80% adherence to the protocol (defined as the degree to which participants are willing and able to complete the 30-minute VR exposure), and >80% completed data (measured by percent data collected at the study appointment, including pre-, midpoint, and post-VR assessments). Acceptability will be demonstrated by 80% of participants reporting VR satisfaction on the Client Satisfaction Questionnaire (mean score of 7/8). Safety of the VR protocol will be demonstrated by 80% of participants completing the VR session without significant side effects, such as motion sickness, dizziness, headache, and nausea.

Aim 2: Collect initial data on the impact of VR Blue on pain, tension and distress, and describe the relationship between pre- to post-VR changes in cognitive variables (i.e., pain catastrophizing, pain self-efficacy) and changes in pain, tension and distress over the course of the VR session.

Hypothesis: 2A. Reductions in pain, tension and distress will be demonstrated during the VR session in colorectal cancer patients. 2B. Pre- to post-VR reductions in pain catastrophizing and increases in pain self-efficacy will be correlated with improvements in pain, tension and distress occurring over the course of the VR session.

Aim 3: Gather qualitative post-session data on patients' experiences, thoughts and feelings about VR to optimize VR Blue for a future randomized clinical trial testing a multi-session VR protocol.

Hypothesis: This data will lead to optimization and manualization of a multi-session VR Blue protocol to manage pain in advanced colorectal cancer patients that can be tested in a larger, randomized clinical trial.

Background & Significance

Colorectal cancer is one of the most common cancers with an estimated nearly 150,000 new cases diagnosed in 2019 and over 50,000 deaths across the United States.¹ It is the fourth most commonly diagnosed malignancy and the second leading cause of cancer mortality.^{1,2} Advanced stage (stage IV) cancers are associated with the highest cancer mortality and morbidity rates for adults in the United States;³ advanced colorectal cancer causes over half a million deaths every year.⁴

Many advanced colorectal cancer patients report high levels of pain and psychological distress to be especially burdensome consequences of cancer.⁵⁻¹⁰ These symptoms are persistent and debilitating for patients, and negatively impact overall quality of life.^{5,11-13} Despite their prevalence, these symptoms often are not adequately treated in advanced cancer patients. Traditional analgesic and other medication regimens for pain and symptom management often do not fully relieve symptoms and cancer patients report significant side effects (e.g., constipation, nausea, sedation) that limit their use of these medications.^{14,15} Non-pharmacological pain management strategies are needed to treat pain and

pain-related symptoms in advanced stage cancer patients. VR could represent a valuable addition to our current armamentarium of treatments for persistent pain in palliative care patients.

Recent evidence suggests Virtual Reality (VR) interventions can lead to reductions in pain for patients with acute pain conditions.¹⁶⁻²¹ VR has not been widely tested in patients with persistent pain, though VR provides individuals with an immersive computer-generated environment that can reduce persistent pain and pain-related tension and distress.¹⁸ Due to their late-stage disease and persistent pain, many advanced colorectal cancer patients report negative pain-related cognitions (e.g., pain catastrophizing) and low confidence that they can control pain (e.g., self-efficacy for pain management). VR may be particularly useful for advanced colorectal cancer patients having persistent pain in that it can impact cognitive pathways by decreasing pain catastrophizing and increasing pain self-efficacy to improve pain control and moderate pain signaling.¹⁶ These cognitive pathways have been shown to be important for pain reduction within the context of cognitive-behavioral pain management protocols.

Our group (Drs. [name] and [name]) has a long track record of developing novel cognitive-behavioral treatment protocols for managing persistent disease-related pain (e.g., pain due to cancer and arthritis).²²⁻³⁰ Our experience in moving treatment protocols from the pilot trial phase to rigorous efficacy and effectiveness trials and into clinical practice enhances the likelihood that the proposed study will successfully lead to a program of VR research in advanced cancer patients. The involvement of [name] (an internationally recognized pain researcher and study consultant) who has conducted research on VR Blue in healthy volunteers and provided input into the design of this study further enhances the likelihood that useful findings will emerge from the proposed study.

The objective of this pilot work is to gather initial data on advanced colorectal cancer patients' immediate response to a single VR session. This preliminary data will be used to optimize VR Blue for future study testing the efficacy of a multi-session VR protocol for managing pain in advanced colorectal patients.

Design & Procedures

Overview of Study Design. We will examine the feasibility, acceptability, safety, and impact of exposing patients to a single 30-minute virtual underwater/sea environment (VR Blue) for reducing pain and pain-related symptoms in patients with advanced stage colorectal cancer.

Selection of Subjects. Participants will include 20 adult colorectal cancer patients with advanced stage disease recruited from the gastrointestinal oncology clinic at the Duke Cancer Institute and from Duke Regional. Eligibility criteria include: a) age 21-85, b) stage IV cancer diagnosis, c) moderate clinical pain documented in medical chart (>4 on 0-10 scale) and confirmed on the day of their study appointment (>4/10), d) ability to read and speak English, e) self-reported normal or corrected to normal vision, and f) self-reported normal hearing. Patients will be excluded if they have: a) a serious mental illness (e.g., schizophrenia, bipolar disorder), b) a medical condition that contraindicates safe participation (e.g., recent myocardial infarction), or c) visual, hearing, or cognitive impairment that will interfere with their ability to engage in VR. Patients will NOT be excluded if they report pain under <4/10 on the day of the study appointment. If they have already arrived to their in person session and do not report pain at a

>4/10, they will not be considered ineligible or turned away; we will still move them through the VR Blue intervention protocol if they are otherwise eligible.

Recruitment. Participants in this study (N=20) will be patients with stage IV colorectal cancer recruited from the Duke Cancer Center in Durham, NC and the Duke Regional Hospital in Durham, NC. Oncology physician champion and gastrointestinal medical oncology clinical lead, [name], MHS (see letter of support) will assist with recruitment. Potential participants will be identified based on a stage IV cancer diagnosis. To assess eligibility, basic patient information will be gathered through the use of electronic medical records (i.e., DSR/DEDUCE) under a Waiver of Consent and HIPAA authorization. In accordance to the Duke guidelines, study staff will contact patients to discuss their interest in the study without first approaching their physician for approval. Potential participants will be asked: a) About their pain with the questions, "Have you had pain on most days of the month for the past 3 months?" and, asked on the day of the scheduled study appointment (Procedures), "Do you have pain today at a 4 or greater on a scale from 0-10?" They must answer "yes" to both questions to be eligible; b) A 6-item Mini-Mental State Exam ("Orientation" and "Registration" subscales). If the participant gets more than 2 items wrong they will be excluded; and c) About their vision and hearing. They will be asked "Do you have moderate or severe problems reading text on a page or computer screen even when you are wearing reading glasses?" and "Do you have moderate or severe problems with your hearing even when you are using a hearing aid?" They must answer "No" to both questions to be eligible. Patients who meet this eligibility criteria and express interest in the study will be recruited and scheduled for a study appointment at the study team's lab (Procedures).

Procedures. Study Appointment. The study appointment will take place at the Duke Pain Prevention and Treatment Research Program office. At this appointment, research staff will explain study procedures and conduct informed consent. Once informed consent is obtained, patients (N=20) will complete the pre-VR assessment (<30 min) via REDCap, a HIPAA/PDPA compliant, web-based survey system. Following completion of this assessment, participants will complete the VR exposure and the midpoint assessment. Participants will then complete the post-VR assessment immediately following VR Blue exposure. Participants will be compensated \$40 for completing this study appointment. Participants will continue to receive usual care and will not be asked to change or decline any strategies for pain management.

Virtual Reality Exposure. We will gather preliminary data on participants' response to a single 30-minute laboratory-based virtual reality underwater/sea environment (VR Blue) session. VR Blue is an immersive computer-generated environment featuring calming scenic graphics and relaxing nature music. VR Blue has been shown to increase tolerance for thermal pain stimuli in healthy participants by [name], consultant on this application. In the proposed study, a member of the study team will familiarize the participant with the VR glasses and screen, and guide them through a demonstration of the VR environment. Participants will be oriented to the VR's video and auditory stimuli with an emphasis on becoming relaxed and fully immersed in the virtual environment. Participants will be instructed to pay close attention to the virtual environment around them to cultivate their awareness of what they see. Following this orientation, the participant will complete the 30-minute VR exposure. At the midpoint, participants will be asked to provide ratings of pain, tension and distress.

Study Measures. Aim 1: Feasibility will be assessed by examining (a) study accrual (N=20 over 6 months), (b) protocol adherence (>80% adherence to the protocol [defined in this study as the degree to which participants are willing and able to complete the 30-minute VR exposure]), and (c) completed data (>80% data collected at the study appointment, including pre-, midpoint, and post-VR assessments). Acceptability will be assessed post-VR using the Client Satisfaction Questionnaire.³¹ Safety of the VR protocol will be assessed based on participants' report of VR side effects, such as motion sickness, dizziness, headache, nausea, or other negative physical reactions. Aim 2: Pre-, midpoint- and post-session ratings of pain, tension, stress, anxiety, and mood. Pain. Pain will be assessed using the Brief Pain Inventory (BPI) measuring pain severity and interference. This measure has been widely used in cancer patients. Tension, Stress, Anxiety and Mood. Tension, stress, anxiety and mood will be measured with Visual Analogue Scale (VAS) items with ratings ranging from 0 to 100. The timeframe reference will be "right now". VAS's for measuring tension, stress, anxiety and mood have been used in prior VR studies. Pre- and post-session measures of expectancy and enjoyment. We will use Visual Analogue Scale (VAS) items with ratings ranging from 0 to 100 to measure how much participants expect to improve from participating in the VR Blue intervention (pre) and how much they enjoyed participating in the VR Blue intervention (post). Pre- and post-session measures of pain catastrophizing and self-efficacy for pain. Pain Catastrophizing. Pain catastrophizing will be measured with the Coping Strategies Questionnaire's Pain Catastrophizing subscale. The timeframe reference will be "right now". Items will be rated on a scale ranging from 0=never do to 6=always do when in pain. Pain Self-Efficacy. Self-efficacy will be measured using items adapted from the self-efficacy for pain management subscale of the Chronic Pain Self-Efficacy Scale. For example, participants will be asked, "How confident are you that you could use virtual reality to decrease your pain?" Items are rated on a 10-point scale ranging from 10=very uncertain to 100=very certain. Scores are averaged to give an overall value for pain self-efficacy. Aim 3: We will conduct exit interviews with participants to collect qualitative data to refine and improve the VR protocol.

Data Analysis and Statistical Considerations. Analyses for Aim 1. Feasibility will be assessed by examining accrual, adherence and data completion. Accrual will be indicated by meeting the recruitment goal of 20 participants in 6 months. Descriptive statistics will be used to report the number of patients screened and determine rates of non-eligibility and refusal. Adherence for patients who are accrued to the study will be examined by calculating the degree to which participants are willing and able to complete the 30-minute VR exposure. 80% completed will serve as our feasibility benchmark. If less than 20% of consented patients complete the 30-minute VR exposure, the VR Blue protocol will not be considered feasible. Data completion will be measured by percent data collected at the study appointment, including pre-, midpoint and post-VR exposure assessments. 80% completed data will serve as our feasibility benchmark. If less than 20% of consented patients have complete data, the VR Blue protocol will not be considered feasible. Acceptability will be indicated by 80% of patients reporting satisfaction with VR Blue (mean score of 7 out of a total 8) on the Client Satisfaction Questionnaire. Safety of the VR protocol will be demonstrated 80% of participants completing the VR session without significant side effects, such as motion sickness, dizziness, headache, nausea, or other negative physical reactions. Analyses for Aim 2. We will examine descriptive data to explore pre-, midpoint and post-VR exposure changes in pain, tension and distress scores. We will cautiously examine these differences in the context of minimally clinically important differences (MCIDs) for pain, tension and distress (e.g., 30% decrease in pain).³⁶⁻³⁹ Correlations will be conducted to provide preliminary data on how pre- to post-VR changes

in two key cognitive variables (i.e., pain catastrophizing, pain self-efficacy) are related to improvements in pain, tension and distress occurring over the VR session. Analyses for Aim 3. Qualitative exit interview data will be coded using open coding and memoing by the study team to generate repeated concepts. These results will be categorized into major themes through selective coding methods. Grounded Theory methods will be used to evaluate the data gathered from the exit interviews.^{40,41} Results will be used to refine and improve the VR protocol for future studies. [name] (co-I) has used Grounded Theory in development of other psychosocial interventions for patients with cancer.

Risk/Benefit Assessment

Risks associated with the proposed study are minimal and not expected, but nonetheless will be carefully monitored. First, due to the use of virtual reality there is the potential for “cybersickness,” a type of motion sickness involving feelings of nausea, eyestrain and/or dizziness. Anticipated risks associated with cybersickness are comparable to typical “everyday” use of computers. If the participant begins to feel any effect of this type, he/she may immediately stop the stop the VR exposure. Patients will be asked to report these symptoms and will have the option of discontinuing participation if these symptoms are problematic. Second, participants may experience anxiety or distress due to questioning about thoughts, feelings, and/or their experience with pain. Again, participants will have the option to discontinue participation if they experience such problems in completing the measures. Third, there is also the possibility of a breach of confidentiality. The informed consent process will address this possibility. All efforts will be made for confidentiality to be maintained by using study ID numbers to identify participants’ research records and by having a limited number of individuals who have access to identifying information. Identifying information will be kept separate from research records. All research records will be kept in a locked file cabinet and password protected computer files. Only the PI and other trained research staff will have access to the research records.

All patients in the trial will continue their usual medical care during the course of the trial, thus their doctors will provide monitoring of the patients’ overall medical status. Participants will not be asked to change or decline any strategies for pain management.

In terms of study benefits, participants may gain an enhanced ability to cope with pain and pain-related distress as a result of participating in this study. Further, participants may experience decreases in symptom severity.

The proposed significance of study findings outweighs the risks. The long-term goal of this research is to improve quality of life in advanced colorectal cancer patients by decreasing pain, tension and distress. This project will provide preliminary data that will be used to inform and optimize development of a multi-session VR protocol to be tested in patients with advanced stage colorectal cancer that could be generalizable to other palliative care populations with pain.

Data & Safety Monitoring

All research personnel who have direct contact with patients will be trained to observe and report any adverse events and unanticipated problems to the PI ([name]). The PI will review with her mentor, a

senior investigator, and will immediately report any safety/adverse events to the institutional review board at Duke University and to PCRC and NINR. An adverse event is defined as any untoward medical occurrence during the clinical investigation that has a causal relationship to the study protocol. A serious adverse event is defined as any event which results in death, is immediately life threatening, results in persistent or significant disability/incapacity, patient hospitalization, or is serious for any other reason representing significant hazard.

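### The 80% rule is the only test of safety, so the plan could call VR Blue safe after a related serious adverse event or with 4 of 20 participants failing

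*Combined protocol and SAP*

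**What the plan says.** The safety rule appears twice. Under Purpose of the Study, the Aim 1 hypothesis reads "Safety of the VR protocol will be demonstrated by 80% of participants completing the VR session without significant side effects", with motion sickness, dizziness, headache and nausea as examples. Under Data Analysis and Statistical Considerations, the Aim 1 paragraph repeats it ("Safety of the VR protocol will be demonstrated 80% of participants completing the VR session without significant side effects") and extends the examples to other negative physical reactions.

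Study Measures gives the data source: "Safety of the VR protocol will be assessed based on participants' report of VR side effects". Neither that section nor the other two says what makes a side effect significant, and none gives a severity grade or a separate limit for serious events.

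The sample size is fixed under Selection of Subjects: "Participants will include 20 adult colorectal cancer patients with advanced stage disease". It is an accrual goal. No error rate, power or reference rate is attached to the safety criterion.

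Data & Safety Monitoring treats serious events separately. It begins its definition "A serious adverse event is defined as any event which results in death, is immediately life threatening" and goes on to disability, hospitalization and other significant hazard. It has the principal investigator review events with a senior mentor and says that she "will immediately report any safety/adverse events to the institutional review board at Duke University", as well as to two further bodies. It does not mention the Aim 1 safety conclusion.

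**The concern.** The rule reduces each participant to a single yes or no, and one percentage then decides whether safety has been demonstrated. A participant hospitalized because of the session and a participant with marked nausea count the same: one failure each. The monitoring section governs what staff do when a serious event happens. It does not govern what the study concludes.

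An analyst following the plan exactly could therefore be obliged to report demonstrated safety alongside a related serious event. Separately, the threshold is loose for the strength of the claim. With 20 participants, a bare pass is compatible with a true failure rate well above 20%. What 20 single sessions can describe is how well one session is tolerated, and the plan labels this as safety.

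**Working it through.** **Inputs from the documents.** N = 20 (Selection of Subjects). Benchmark 80% (Aim 1 hypothesis and Aim 1 analysis). A success is a participant who completes the session without significant side effects, so a failure is either a significant side effect or non-completion for any reason.

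**Inputs not in the documents.** No expected side-effect rate, reference rate, alpha or power is given for safety. There is thus no derived figure to reproduce, and the true rates below are assumptions shown over a range.

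**Step 1: the rule in counts.** 0.80 × 20 = 16 successes needed, so 20 − 16 = 4 failures are allowed. The adherence and data-completion benchmarks carry a greater-than sign in the Aim 1 hypothesis, but the safety benchmark does not, so I read it as at least 80%. A strict reading would need 17 and allow 3.

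**Step 2: a single serious event.** One participant with a related serious event and 19 uneventful sessions gives 19/20 = 95%, a pass. That event can affect the result only if at least 4 other participants also fail.

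**Step 3: precision (Clopper-Pearson).** For x failures in n, the lower limit is the 0.025 quantile of Beta(x, n − x + 1) and the upper limit is the 0.975 quantile of Beta(x + 1, n − x).

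| Failures / 20 | Observed | Exact 95% interval |
|---|---|---|
| 0 | 0% | 0% to 16.8% |
| 1 | 5% | 0.1% to 24.9% |
| 4 | 20% | 5.7% to 43.7% |

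For 4/20 the limits come from Beta(4, 17) and Beta(5, 16). For 0/20 the upper limit is 1 − 0.025^(1/20) = 0.168.

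**Step 4: chance of passing.** P(pass) = P(X ≤ 4), where X is Binomial(20, q) and q is the assumed true failure rate.

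| Assumed q | P(pass), 16 needed | P(pass), 17 needed |
|---|---|---|
| 5% | 0.997 | 0.984 |
| 10% | 0.957 | 0.867 |
| 20% | 0.630 | 0.411 |
| 30% | 0.238 | 0.107 |
| 40% | 0.051 | 0.016 |

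**Step 5: the rule against serious events alone.** Suppose, for illustration only, that serious events are the only failures. At an assumed rate of 5%, at least one occurs with probability 1 − 0.95^20 = 0.64, and the rule still passes with probability 0.997. At an assumed 1%, at least one occurs with probability 1 − 0.99^20 = 0.18, and the chance of passing is higher still. At either rate the criterion is almost blind to them.

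**The case against.** The best defence is that the rule was never meant for serious events. Its examples are cybersickness symptoms, it rests on participant report, and serious events have their own section with definition, review and immediate reporting. That is a fair account of the likely intent, and a reader should not infer that the plan ignores serious events in conduct. It does not close the gap. The wording of the rule is open-ended, no sentence excludes serious events from it, and no other criterion brings them into the safety conclusion.

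A reader might also infer that the benchmark contradicts Risk/Benefit Assessment, which says "Risks associated with the proposed study are minimal and not expected, but nonetheless will be carefully monitored" and "Anticipated risks associated with cybersickness are comparable to typical “everyday” use of computers". The documents do not support that. Those sentences state an expectation without a rate, whereas the 80% figure is a minimum. Expecting little harm and tolerating up to a limit are compatible, and the same section openly names nausea, eyestrain and dizziness as possible.

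A third tempting reading is that a pass at 16/20 means that 20% had significant side effects. It means at most 20%, because a participant who stops for an unrelated reason also fails. The 5.7% to 43.7% interval therefore describes failures of the composite.

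It can also be said that this is a pilot of one session, described as preliminary. That stands, and it limits the consequences: the documents say that the data will inform a later multi-session protocol, but they do not make the safety verdict a condition for it. The limit of 16.8% at 0/20 applies to any study of this size. It argues for a narrower claim, not for a larger study.

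**Conclusion.** The concern holds as a gap between a decision rule and the claim attached to it. The 80% criterion is the sole basis for saying safety is demonstrated, and serious adverse events have no part in it. As written, the claim would be made at 19/20 with one related serious event, and at 16/20 with up to 4 participants failing through side effects or non-completion. Across assumed true failure rates of 10% to 40%, the chance of passing runs from 0.96 to 0.05; at 30% it is 0.24.

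These figures assume 20 evaluable participants, independence between them, and the at-least-80% reading. The strict reading lowers the pass probabilities (0.87 to 0.016 over the same range) but does not bring serious events into the rule. The point does not rest on any conflict with the risk section, or on a belief that serious events are likely in a single session. It is worth correcting, and it does not call the design into question.

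**What to change.** Amend the safety sentence in the Aim 1 hypothesis and in the Aim 1 analysis paragraph, in the same words in both places.

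1. Describe the 80% criterion as a benchmark for short-term tolerability of one session. In place of the statement that safety is demonstrated, report the observed proportion of participants with significant side effects and its exact 95% interval. Show non-completion for other reasons separately.
2. State that serious adverse events are summarised separately in the Aim 1 results, and that no safety conclusion is drawn from the 80% figure if a serious event is judged related to the session.

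The sample size, procedures and treatment of participants do not change, and side effects and completion are already to be recorded. The costs are a less favourable stated claim and a judgement of relatedness for each serious event. The second is small, because the adverse event definition under Data & Safety Monitoring already turns on a causal relationship to the protocol. One limit remains: the reported proportion will be only as reproducible as the meaning given to a significant side effect, which the plan leaves undefined.

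### The appointment-day pain question shows patients the cut-off before the only pain baseline is taken, which may inflate some baselines and overstate the Aim 2 fall

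*Combined protocol and SAP*

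**What the plan says.** All references are to the Combined protocol and SAP, mostly within Design & Procedures.

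- **Recruitment.** On the day of the appointment, potential participants are asked "Do you have pain today at a 4 or greater on a scale from 0-10". A companion question covers pain over the past 3 months. Of the two, the section says "They must answer 'yes' to both questions to be eligible".
- **Selection of Subjects.** Pain above 4/10, confirmed on the day, is listed as an eligibility criterion. The same section then says "Patients will NOT be excluded if they report pain under <4/10 on the day of the study appointment", and that patients who have already arrived with low pain "they will not be considered ineligible or turned away".
- **Procedures.** The baseline follows consent at the same appointment: "Once informed consent is obtained, patients (N=20) will complete the pre-VR assessment (<30 min) via REDCap". Completing the appointment is paid at $40.
- **Study Measures.** "Pain will be assessed using the Brief Pain Inventory (BPI) measuring pain severity and interference". Pain is rated before, midway through and after the session.
- **Data Analysis and Statistical Considerations, Aim 2.** Changes across the three ratings are described, with no comparator, and read cautiously against benchmarks such as a "30% decrease in pain". Under Purpose of the Study, Hypothesis 2A predicts a reduction during VR.

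**The concern.** The question tells the patient which answer qualifies, on the day the baseline is taken. Someone who wants the session or the payment has a reason to say yes. Having claimed pain of at least 4, that person may then give a BPI rating that fits the claim. The eligibility pressure belongs to the period before VR, so any inflation that has faded by the midpoint or post-VR rating would look like relief.

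With one arm, nothing in the design separates such an artefact from an effect of VR. It would enter the pre-to-midpoint and pre-to-post changes, and the count of patients who pass the 30% mark. These data are meant to shape VR Blue for a later efficacy study, and cautious reading afterwards cannot recover a baseline taken without the cue.

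**Working it through.** The plan gives no figure for baseline inflation and no sample-size derivation, so there is nothing to reproduce. The calculation below only shows what inflation of a given size would do.

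**Inputs from the document:** 20 participants; a cut-off of 4 on a 0-10 scale; a 30% benchmark.

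**Assumptions:** pain is analysed as a 0-10 rating (the plan does not say which BPI score is used); there is no true change; *k* patients inflate baseline by *d* points; the inflation is gone at the later rating. I take *k* = 2 to 5 and *d* = 1 to 2.

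**Overstatement of the mean fall** = *k* × *d* / 20

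| | *d* = 1 | *d* = 2 |
|---|---|---|
| *k* = 2 | 2 × 1 / 20 = 0.1 | 2 × 2 / 20 = 0.2 |
| *k* = 5 | 5 × 1 / 20 = 0.25 | 5 × 2 / 20 = 0.5 |

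If a fraction *p* of the inflation persists at the later rating, each figure is multiplied by (1 − *p*). With *p* = 0.5 the range becomes 0.05 to 0.25.

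**One patient's apparent percentage fall** = *d* / reported baseline

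- Reported 4, true 3: 1 / 4 = 25%, below the benchmark.
- Reported 4, true 2: 2 / 4 = 50%, above it.
- Inflation needed for a false 30% fall = 0.3 × reported baseline: 1.2 points at 4, 1.5 at 5, 1.8 at 6 and 2.1 at 7.

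So 2 to 5 patients going from a true 2 to a reported 4 would make 2/20 = 10% to 5/20 = 25% of the sample false responders. The same number going from 3 to 4 would add none. A patient with a genuine fall short of 30% could be carried over the mark by less inflation than these thresholds.

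**Group mean as a percentage.** Let *x* be the average inflation over all patients and take a true mean of 4. The apparent fall is *x* / (4 + *x*).

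- 2 of 20 by 1 point: 0.1 / 4.1 = 2.4%.
- 5 of 20 by 2 points: 0.5 / 4.5 = 11.1%.
- To reach 30%: *x* = 0.3 × 4 / 0.7 = 1.71 points. At 2 points each this needs 1.71 / 2 = 86% of patients, or 18 of 20.

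**The case against.** The strongest reply is that the documents themselves weaken the motive. Selection of Subjects says that patients who arrive with low pain still go through the session. On that text, a no given on site costs neither the VR session nor the payment. This stands, but only as far as patients know it. The document does not say whether they are told that rule or told that the answer decides eligibility, and the consent form is not available to check. Recruitment still requires a yes. The reply also helps the fix: if a low rating does not bar an arrived patient, stating the cut-off at the visit serves no purpose.

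Several stronger readings are tempting but not supported:

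- **That the question comes immediately before the baseline rating.** Only the same day is stated. The hour and mode are not given, and explanation of procedures and consent precede the pre-VR assessment.
- **That a yes at screening fixes the BPI rating at 4 or more.** The BPI is a separate instrument. Carry-over is an inference.
- **That later ratings are free of the cue, so the bias can only run one way.** A wish to be consistent could also hold up the midpoint rating, which would shrink the artefact.
- **That the cue puts a shared error into the Hypothesis 2B correlations.** Baseline inflation enters the pain change. No mechanism puts the same error into the change in catastrophizing or self-efficacy, and error in one variable alone would tend to weaken a correlation.

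It is also fair to say that this is a 20-patient pilot, that Aim 2 is descriptive, and that the Aim 1 benchmarks do not depend on pain change.

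**Conclusion.** The point holds as a modest, avoidable risk of bias. The document does reveal the cut-off in a closed question on the appointment day and does make a yes a condition in one place. The pre-VR BPI at that appointment is the only baseline for an uncontrolled change.

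The size is unknown. Under the assumed 1 to 2 points of inflation in 2 to 5 of 20 patients, fully gone by the later rating, the mean fall is overstated by 0.1 to 0.5 points. With no true change, false individual responders appear only from 1.2 points of inflation at a reported 4, and more at higher ratings. A reader might infer that the cue could by itself produce a 30% fall in the group mean. The arithmetic does not support that without large and nearly universal inflation. The documents do not show that any patient would inflate. They show that the cue is present, and removing it costs very little.

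**What to change.** - Replace the closed question with an open rating that states no cut-off, for example: 'What is your pain right now, from 0 to 10?' Record the number.
- Do not disclose the cut-off to patients, at recruitment contact or at the visit.
- Reconcile the day-of pain statements: above 4 confirmed on the day, a required yes to 4 or greater, and no exclusion for low pain on the day. Staff then apply whatever rule remains to the recorded number. The rewording works under any of them.
- Keep the screening rating separate from the pre-VR BPI. Applying a pain rule to the BPI would select patients on the outcome baseline and place that decision after consent.
- Report how many participants were below the cut-off.

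**Cost:** one reworded screening question and one recorded number. More participants may be recorded below the cut-off, and the observed pain reduction may be slightly smaller. The change does not supply a comparator, so any remaining fall still cannot be attributed to VR alone.
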